#### 5.6.6.2 Doppler Sonography

The results from Doppler Sonography will be presented in the listings only.

#### 5.6.6.3 Platelet Function Test

For each parameter of platelet function assessed via flow cytometric markers, the actual value and changes from baseline will be summarized by visit and treatment group using descriptive

statistics. Analysis of changes from baseline will be based on the number of subjects with both nonmissing baseline and relevant postbaseline results.

Only listings will be provided for platelet function assessed using platelet aggregometry.

## 5.7 OTHER ANALYSES

### 5.7.1 Health Outcome Economics Analyses

Health outcome economics data will be listed in the subject data listings only.

## 5.8 EXPLORATORY ANALYSES

Exploratory analyses may be conducted as appropriate. Any exploratory analyses that are performed will be appropriately titled/labeled as exploratory and will be clearly distinguished from planned analyses when results are reported in the Clinical Study Report.

## 5.9 EXTENSION PHASE ANALYSES

Not applicable.

## 6 INTERIM ANALYSES

No interim efficacy analysis is planned for this study, and therefore no adjustment of the *P*-value for the final efficacy analysis is needed. However, to protect subjects' safety, an independent DSMB will be established to monitor the ongoing safety data in unblinded manner. To maintain the blinding of DSMB members on the efficacy data, no platelet transfusion data, by-subject listing on platelet count, and by-visit summary on platelet count and change from baseline in platelet count will be sent to DSMB. The only information DSMB will receive on platelet count is the percentage of subjects with extreme values (eg, exceeds  $200 \times 10^9/L$ ) for safety reason. The DSMB safety interim analysis will be performed by an independent statistician and governed by an external DSMB. To maintain the blinding and integrity of the study, procedures will be implemented to ensure the DSMB and independent statistician have sole access to unblinded interim safety data.

Full details of the DSMB procedures including primary responsibilities of the DSMB, its relationship with other study components, its membership, and the purpose and timings of its meetings will be documented in a DSMB charter. These details will also include procedures to ensure confidentiality and proper communication, the guidelines to be implemented by the DSMB, and an outline of the content of the closed reports (unblinded) and open reports (blinded) that will be provided to the DSMB.

## 7 CHANGES IN THE PLANNED ANALYSES

SAP version (Final 2.0) is updated based on Protocol Amendment 04 with the following changes:

- Sections 3.1.2, 3.1.3, 5.1.2, 5.1.3, 5.3.3.1, 5.4.2, 5.4.2.3, 5.4.3 and 5.4.3.5: Efficacy endpoint "Proportion of subjects with a WHO bleeding score  $\geq 2$  after randomization and

up to 7 days following an elective procedure” is moved from secondary to exploratory endpoint to match the protocol amendment 4. These sections have been updated to reflect this change.

- Section 4: Sample size is reduced from 300 to 200. This section has been updated to match the protocol amendment 4.
- Section 5.4.2.2: Calculation of 95% CI for change from baseline in platelet count on Procedure Day for each treatment group within each baseline platelet count cohort has been removed to ensure consistency with the study objectives.
- Section 5.7.1: This section is updated to reflect that only listings will be provided for the Health Economics Assessment.
- Section 5.2.1: Per-Protocol exclusion criteria are finalized.

SAP version (Final 2.0) is also updated based on Protocol Amendment 02 with the following changes:

- Section 3.2 table 1, and sections 5.2.4, 5.3.2, 5.3.4, 5.4.1, 5.4.1.2 and 5.4.2.1: Categorization of risk of bleeding is updated to match protocol amendment 02
- Section 5.6.6.3: Listing of platelet function test assessed using platelet aggregometry has been added.
- Section 13.1: "Fasting Glucose value" has been added to the criteria for determining grade 3 and 4 in the lab grading table.

SAP version (Final 2.0) is also updated from version Final 1.0 to ensure consistency with the eCRF/protocol as follows:

- Section 5.6.5: ECG interpretation category is updated.
- Section 5.2.4: Baseline summaries of creatinine clearance and disease etiology, and subgroup analysis by disease etiology have been added.

## 8 DEFINITIONS AND CONVENTIONS FOR DATA HANDLING

### 8.1 VISIT WINDOW

Study Day 1 is defined as the date of the first dose of study drug. The analysis visits defined below will be used in the by-visit summaries:

Visit	Target Visit Date	Visit Window	Analysis Visit
Visit 2 (Baseline)	Study Day 1	Less or equal to Study Day 1	Last visit on or before Study Day 1
Visit 3	Study Day 4	Study Day 2 to 7	Closest visit to Study Day 4
Visit 4	Study Day	Subjects with procedure:	Subjects with platelet

Visit	Target Visit Date	Visit Window	Analysis Visit
(Procedure Day)	10 to 13	Study Day 8 to actual procedure day  Subjects without procedure: Study Day 8 to 13	transfusion: last visit before transfusion  Subjects with procedure but without transfusion: last visit before procedure  Subjects without platelet transfusion or procedure: closest visit to Study Day 10
Visit 5	7 Days post procedure	Subjects with procedure: 1 to 10 days post actual procedure day  Subjects without procedure: Study Day 14 to 20	Subjects with procedure: visit closest to 7 days post actual procedure day  Subjects without procedure: closest visit to Study Day 17
Visit 6	Study Day 35	Subjects with procedure: Greater or equal to actual procedure day +11 days  Subject without procedure: Greater or equal to Study Day 21	Closest visit to Study Day 35

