9.1.2.3 Procedure Day (Visit 4)

This will occur 5 to 8 days after the last dose of study drug (on Study Day 10 to 13).

All Procedure Day assessments are to be completed prior to the procedure and include assessments shown in [Section 9.5.2.1 \(Table 5\)](#).

In addition, all subjects are required to return study drug and the dosing diary at this visit.

The elective procedure for those subjects whose preprocedural platelet count is $>200 \times 10^9/L$ on Visit 4 (Procedure Day) may be delayed at the discretion of the investigator until platelet counts are below $200 \times 10^9/L$. All subjects whose platelet count exceeds $200 \times 10^9/L$ will be required to have a Doppler assessment at Visit 5. For any subjects where the presence of a PVT is suspected, confirmation of diagnosis, via CT scan or MRI, should be performed and treatment for PVT initiated per local guidelines.

Permitted procedures and the risk of bleeding associated with each procedure are listed in [Table 1](#). It is planned that no fewer than 10% of subjects will be enrolled into the high risk group and no more than 60% of subjects in the low-risk group.

Table 1 Permitted Procedures and the Risk of Bleeding Associated with Each Procedure (revised per Amendment 02)

Risk of Bleeding Associated with Procedure	Procedure
Low risk	Paracentesis
	Thoracentesis
	Gastrointestinal endoscopy with or without plans for biopsy, colonoscopy, polypectomy, or variceal banding
Moderate risk	Liver biopsy
	Bronchoscopy with or without plans for biopsy
	Ethanol ablation therapy or chemoembolization for HCC
High risk	Vascular catheterization (including right side procedures in subjects with pulmonary hypertension)
	Transjugular intrahepatic portosystemic shunt
	Dental procedures
	Renal biopsy
	Biliary interventions
	Nephrostomy tube placement
	Radiofrequency ablation
	Laparoscopic interventions

Level of risk based on KOL input and Malloy PC, Grassi CJ, Kundu S, Gervais DA, Miller DL, Osnis RB, et al. for the Standards of Practice Committee with Cardiovascular and Interventional Radiological Society of Europe (CIRSE) Endorsement. Consensus Guidelines for Periprocedural Management of Coagulation Status and Hemostasis Risk in Percutaneous Image-guided Interventions (2009)¹⁵

Subjects who have an International Normalization Ratio (INR) >1.6 should be treated with fresh frozen plasma (FFP) or other appropriate therapies, where indicated, as per local guidelines and practices.

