Liver function tests	alanine aminotransferase, alkaline phosphatase, aspartate aminotransferase, direct bilirubin, total bilirubin, gamma-glutamyl transpeptidase
Renal function parameters	blood urea nitrogen, creatinine
Other	albumin, calcium, cholesterol, creatine phosphokinase with fractionation, globulin, glucose, lactate dehydrogenase, phosphorus, total protein, triglycerides, uric acid
Urinalysis	bacteria, casts, crystals, epithelial cells, glucose, ketones, occult blood, pH, protein, RBCs, specific gravity, WBCs
Protocol specified	
Females only	serum beta-human chorionic gonadotropin pregnancy tests, urine pregnancy tests
Platelet function tests ^a	eg, p-selectin and integrin IIbβ3 with and without an agonist. The following agonists will be used: 0.5 μM ADP, 20 μM ADP, 1.5 μM TRAP, or 20 μM TRAP (eg, platelet aggregation with an agonist. ADP will be used as the agonist) (revised per Amendment 02)

ADP = adenosine diphosphate, RBC = red blood cell, TRAP = thrombin receptor agonist peptide, WBC = white blood cell

a: Performed only at selected sites

Clinical laboratory tests during the study will be performed by the designated central laboratory. All blood and urine samples will be collected and sent to the central laboratory on the day of collection unless otherwise instructed. When a hematology test is required, 2 blood samples will be collected: 1 for central laboratory analysis and 1 for local laboratory analysis. Investigators will utilize the platelet count result received from the local laboratory hematology test analysis to qualify subject's entry into the study, and also for clinical assessments.

Only platelet count data from local laboratories, including the date and clock time of collection of the sample, will be collected and entered into the CRF for analysis. All other hematological parameters will be collected and loaded into the database for analysis according to results derived from the designated central laboratory.

A laboratory abnormality may meet the criteria to qualify as an AE as described in this protocol (see Adverse Events and Other Events of Interest) and the CRF Completion Guidelines. In these instances, the AE corresponding to the laboratory abnormality will be recorded on the Adverse Event CRF.

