#### 5.1.2 Secondary Endpoint(s)

The secondary efficacy endpoints are:

- Proportion of responders defined as subjects who achieve platelet counts of  $\geq 50 \times 10^9/L$  on Procedure Day (i.e., prior to receiving a platelet transfusion or undergoing the elective procedure)
- Change from baseline in platelet count on Procedure Day (i.e., prior to receiving a platelet transfusion or undergoing the elective procedure)

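### In a narrow case, SAP 8.1's Visit 4 rule for transfused subjects can select a platelet count that both secondary endpoints exclude

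*SAP*

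**What the plan says.** SAP 5.1.2 defines both secondary endpoints, the proportion reaching 50 × 10⁹/L and the change from baseline, on the Procedure Day count taken "prior to receiving a platelet transfusion or undergoing the elective procedure". SAP 5.4.2 and protocol 9.7.1.1 carry the same restriction.

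SAP 8.1 says how the Visit 4 (Procedure Day) record is chosen. For subjects with a procedure the window is "Study Day 8 to actual procedure day". Within it, the choice depends on transfusion status:

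- Not transfused: "Subjects with procedure but without transfusion: last visit before procedure".
- Transfused: the entry for subjects with platelet "transfusion: last visit before transfusion".

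Visit 5 for subjects with a procedure covers "1 to 10 days post actual procedure day". The table is introduced with the sentence "The analysis visits defined below will be used in the by-visit summaries". SAP 5.4.2.1 and 5.4.2.2 refer to the Procedure Day and give no selection rule of their own.

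On conduct, protocol 9.1.2.3 states: "All Procedure Day assessments are to be completed prior to the procedure". Note g to protocol Table 5 requires the hematology draw to come before platelets are given. Protocol 9.5.1.5 says that local platelet counts, "including the date and clock time of collection of the sample, will be collected and entered into the CRF for analysis".

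**The concern.** The endpoint definition sets two limits on an eligible count: before any platelets and before the procedure. SAP 8.1 applies one limit to each group. Non-transfused subjects are limited by the procedure, transfused subjects only by the transfusion. The transfused-subject entry also does not say that the first transfusion is meant.

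Two kinds of ineligible count can get through. One is a count taken after the procedure but before a later transfusion, which may have fallen through procedural bleeding. The other is a count taken between two transfusions, which may contain donor platelets. The first could turn a responder into a non-responder, and the second could do the reverse. Both secondary endpoints are tested within the alpha-controlled sequence of SAP 5.3.3, so the count that feeds them should follow from the text without interpretation.

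**Working it through.** The plan states no figure on this point, so the check applies the rule as written to example times and compares the result with the endpoint definition.

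**Inputs.** From SAP 8.1: the Visit 4 window, the two selection rules and the Visit 5 window. From SAP 5.1.2: the endpoint restriction. From SAP 4: 67 avatrombopag and 33 placebo subjects per cohort, an 18% placebo response and a 35-point difference.

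**Example subject (hypothetical times).** Procedure on Day 10 at 10:00. Local counts on Day 10 at 08:00 (scheduled Visit 4), Day 10 at 14:00 (unscheduled), Day 11, Day 13 and Day 17. The Visit 4 window admits only the two Day 10 counts, because counts from Day 11 belong to Visit 5.

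| Transfusion | Selected under SAP 8.1 (window and rule) | Required by SAP 5.1.2 |
|---|---|---|
| Day 10, 09:00 | 08:00 | 08:00 |
| Day 10, 11:00 | 08:00 | 08:00 |
| Day 10, 16:00 | 14:00 | 08:00 |
| Day 12 | Day 10, 14:00 | 08:00 |
| Day 14 | Day 10, 14:00 | 08:00 |
| None | 08:00 | 08:00 |

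The rule departs from the endpoint in three rows, and in each of them only because the 14:00 count exists. Without it, every row gives 08:00. The transfusion itself may fall on a later day; the stray count must fall on the procedure day.

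**Two transfusions.** Take the same counts with platelets given at 09:00 and again at 16:00. If the rule means the first transfusion, it selects 08:00. If it means the last, it selects 14:00, after donor platelets and after the procedure. The text does not say which. A recheck between two transfusions that both precede the procedure raises the same ambiguity, and there a procedure limit alone would not resolve it.

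**Selecting before the earlier of the first transfusion and the procedure.** This gives 08:00 in every case above.

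**Size per subject.** One subject whose responder status changes moves a cohort proportion by

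- avatrombopag: 1/67 = 1.5 percentage points
- placebo: 1/33 = 3.0 percentage points

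Status changes only if the wrong and right counts lie on opposite sides of 50 × 10⁹/L. For change from baseline, any difference between the two counts enters the Wilcoxon test, but the documents give nothing from which to size it.

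**Planned non-response.** Placebo: 1 − 0.18 = 82%. Avatrombopag: 1 − (0.18 + 0.35) = 47%. At the planned rates these are upper limits on the share of each arm under the transfused-subject rule, because non-response also counts other rescue procedures and missing outcomes. They do not estimate how many subjects would be affected.

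**The case against.** The strongest reply is that the endpoint definition already governs. SAP 5.1.2 and 5.4.2 exclude these counts, and the SAP 8.1 table is introduced for by-visit summaries, so a careful programmer would not let it override the definition. Conduct closes most of the gap as well: Visit 4 assessments come before the procedure, the blood draw comes before platelets, and the next scheduled count is at Visit 5. A repeat count ordered for bleeding may not be treated as a visit at all. Amendment 04's rationale describes bleeding events as rare. Finally, SAP 9 leaves derivations to separate programming documents, which were not available and may already settle same-day ordering.

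Most of this stands as a limit on size. It does not remove the conflict. No other rule for choosing the Procedure Day count appears in the documents, so using SAP 8.1 for the secondary endpoints is the natural inference. Its wording there differs from the definition it would implement.

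Two stronger readings are tempting and are not supported. A reader might infer that any subject transfused after the procedure could have a much later count used. The window prevents that, because counts from the day after the procedure fall in Visit 5. A reader might also take the 82% and 47% figures as showing an error concentrated on placebo. Those are composite non-response rates. Protocol 7.1 says that platelets are commonly given immediately before procedures, and for a subject transfused once at that point the rule is correct. More transfusion on placebo does not show more post-procedure transfusion with a same-day repeat count, or more repeat transfusion with a count in between.

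**Conclusion.** The conflict between SAP 8.1 and SAP 5.1.2/5.4.2 is real but narrow. It matters only when an extra local count is recorded in the Visit 4 window, is treated as a visit, and falls either after the procedure and before a later transfusion or between two transfusions. The documents give no frequency; few subjects is a judgment, not a derived figure. The effect is 1.5 or 3.0 points on a cohort rate for each subject whose responder status changes. The two mechanisms can push in opposite directions, so the net direction is unknown. An arm imbalance is not established, and no change in any test conclusion is shown.

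The conclusion assumes that the SAP 8.1 table is used to derive the secondary endpoints and that the unseen programming documents do not already correct it. Minor priority: a wording repair to make before unblinding.

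**What to change.** In SAP 8.1, for subjects with a procedure, define Visit 4 as: *the last local platelet count from Study Day 8 onward taken before the earlier of the first platelet transfusion and the start of the procedure*. State that this rule also serves SAP 5.4.2.1 and 5.4.2.2. Where no count qualifies, the missing-data rules already in those sections apply.

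The cost is one line of text and a small programming change, with no effect on sample size or power. Sample clock times (protocol 9.5.1.5) and transfusion start times (protocol 9.5.1.3) are collected. The documents do not say that a procedure clock time is recorded, although the existing rule for non-transfused subjects already needs the same ordering. The sponsor should confirm it. If no procedure time is held, use the scheduled pre-procedure Visit 4 count, provided it precedes the first transfusion.

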9.4.4 Selection of Doses in the Study

Dose selection has been carefully focused on seeking to maintain an appropriate risk:benefit ratio balance in this patient population, removing the requirement for platelet transfusion, or any rescue procedure for bleeding, while minimizing the risk of thromboembolic events. The selected doses, based on modeling and simulation of the E5501-G000-202 study data, are aimed at achieving sufficient efficacy (eliminating the need for platelet transfusion) while specifically limiting the proportion of subjects achieving platelet counts $>200 \times 10^9/L$ to less than 2%.

The current study design employs a dosing regimen according to baseline platelet count that is anticipated to lead to a similar overall rise in platelet counts irrespective of baseline platelet count.

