### 5.4.3 Other Efficacy Analyses

The following efficacy analyses are for exploratory purpose only.

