#### 5.4.3.2 Proportion of responders defined as subjects who achieve platelet counts of $\geq 50 \times 10^9/L$ , $\geq 75 \times 10^9/L$ , or $\geq 200 \times 10^9/L$ at each visit

The number and percentage of responders will be summarized by treatment group within each baseline platelet count cohort at each visit. Missing values will not be imputed.

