### 5.6.3 Laboratory Values

Laboratory results will be summarized using Système International (SI) units, as appropriate. With the exception of urinalysis, platelet function tests and platelet count (which is considered as an efficacy parameter), for all quantitative parameters listed in [protocol Section 9.5.1.5 Safety Assessments \(Laboratory Measurements\)](#), the actual value and the change from baseline will be summarized by visit and treatment group using descriptive statistics. Analysis of changes from baseline will be based on the number of subjects with both nonmissing baseline and relevant postbaseline results.

Laboratory test results will be assigned a low/normal/high (LNH) classification according to whether the value is below (L), within (N), or above (H) the laboratory parameter's reference range. Shifts from baseline (LNH) to Procedure Day and to the end of the Follow-up Phase will be presented for each laboratory parameter. Similar shift tables from baseline (LNH) to the highest/lowest postbaseline LNH classification will also be provided. A subject will be counted once in highest LNH classification and once in the lowest LNH classification.

The Sponsor's Grading for Laboratory Values (see [Appendix 1](#)) presents the criteria that will be used to identify subjects with treatment-emergent markedly abnormal laboratory values (TEMAV). Except for phosphate, a TEMAV is defined as a postbaseline value with an increase from baseline to a grade of 2 or higher. For phosphate, a TEMAV was defined as a postbaseline value with an increase from baseline to a grade of 3 or higher. When displaying the incidence of TEMAVs, each subject will be counted once in the laboratory parameter high and in the laboratory parameter low categories, as applicable.

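### If a recheck after a count above 200 is treated as a visit, the SAP's Visit 4 rule removes the high count from the only final table that uses the 200 threshold

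*SAP*

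**What the plan says.** Counts below are in units of 10⁹/L.

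- **Delay.** Under Protocol 9.1.2.3, when the preprocedural count at Visit 4 is above 200 the procedure "may be delayed at the discretion of the investigator until platelet counts are below" 200.
- **Visit 4 window.** SAP 8.1 sets it, for subjects with a procedure, as "Study Day 8 to actual procedure day". Within it, the value kept is: "Subjects with procedure but without transfusion: last visit before procedure". Where neither a transfusion nor a procedure takes place: "Subjects without platelet transfusion or procedure: closest visit to Study Day 10". The section applies these analysis visits to the by-visit summaries.
- **The 200 threshold in the final analysis.** SAP 5.4.3.2 covers ≥50, ≥75 and ≥200: "The number and percentage of responders will be summarized by treatment group within each baseline platelet count cohort at each visit". The parent section, SAP 5.4.3, adds: "The following efficacy analyses are for exploratory purpose only".
- **Laboratory summaries.** SAP 5.6.3 leaves platelets out of the value and change tables: "With the exception of urinalysis, platelet function tests and platelet count (which is considered as an efficacy parameter").
- **Why 200 matters.** Protocol 9.4.4 says the doses aim at efficacy while "specifically limiting the proportion of subjects achieving platelet counts" above 200 to less than 2%.

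**The concern.** A delay until the count is below 200 implies at least one further count before the procedure. The Visit 4 window stretches with the delay and keeps the last record in it, so the count that triggered the delay can be replaced by one that is below 200 by design. The subjects affected are those whose high count changed their management.

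At stake is a descriptive figure. Dose selection rested partly on holding the proportion above 200 under 2%, because of thrombosis risk (Protocol 7.2, 7.2.1 and 9.4.4). A reader of the final report would look to the ≥200 table to see whether that was achieved.

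**Working it through.** The plan states no figure to reproduce here. The check applies the rule to example subjects, traces each output that could show the high count, and then sets the scale.

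**1. Apply SAP 8.1 (hypothetical non-transfused subjects)**

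| Recorded counts | Procedure | Visit 4 value | Counted as ≥200? |
|---|---|---|---|
| Day 10: 230; Day 13: 180 (treated as a visit) | Day 13 | 180 | No |
| Day 10: 230; Day 17: 185 (treated as a visit) | Day 17 | 185 | No |
| Day 10: 230; recheck not treated as a visit | Day 13 | 230 | Yes |
| Day 10: 230; later recheck | Never done | 230 (closest to Day 10) | Yes |

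The Day 10 value in the first two rows enters no other analysis visit. The Visit 3 window ends on Day 7, and the Visit 5 window starts one day after the procedure.

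**2. Trace the outputs**

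- SAP 5.4.3.2, ≥200: by visit, so it takes the value chosen by 8.1. The count is lost.
- SAP 5.6.3, values and changes: platelets excluded.
- SAP 5.6.3, shifts to the highest classification: even if platelets were included, the cut is the reference range, not 200.
- SAP 13.1 grading: only low platelet counts are graded.
- SAP 6 and Protocol 9.7.3, DSMB: the percentage of subjects with extreme counts, for example above 200. By-visit platelet summaries are withheld from the DSMB, so this is a subject-level figure that 8.1 does not by its terms govern. It could capture the count. It is interim, and the SAP does not say it is repeated in the final report.
- Visit 5 Doppler: required when the preprocedural count exceeds 200 (Protocol Table 5, footnote l), so it marks these subjects indirectly without giving the count. The protocol synopsis says Doppler is summarized by treatment group; SAP 5.6.6.2 gives listings only.

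**3. Scale**

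Inputs: 67 avatrombopag subjects per cohort and 133 in total (SAP 4); the design aim of less than 2%.

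- One subject in a cohort: 1/67 = 1.49 points. If only 60 had a Visit 4 count (an assumption; 5.4.3.2 does not impute), 1/60 = 1.67 points.
- One subject among all avatrombopag subjects: 1/133 = 0.75 points.
- The 2% line: 0.02 × 67 = 1.34 subjects per cohort; 0.02 × 133 = 2.66 subjects in total.
- Losing one subject can move the displayed figure across 2%: 2/67 = 2.99% becomes 1/67 = 1.49%; pooled, 3/133 = 2.26% becomes 2/133 = 1.50%.
- Exact (Clopper-Pearson) 95% intervals: 0/67, 0 to 5.4%; 1/67, 0.04 to 8.0%; 2/67, 0.4 to 10.4%. All include 2%.

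For an assumed true rate p of Visit 4 counts above 200, the expected number per cohort is 67p and the chance of at least one is 1 − (1 − p)^67:

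| Assumed p | Expected in 67 | Chance of at least one |
|---|---|---|
| 0.5% | 0.34 | 29% |
| 1% | 0.67 | 49% |
| 2% | 1.34 | 74% |

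At p = 2% the chance of three or more in a cohort is 15%. At each assumed rate these chances are upper limits for the problem arising, because a delay, no transfusion and a recorded recheck treated as a visit are also needed.

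**The case against.** The strongest reply is that the loss is conditional on text not provided. SAP 8.1 does not say whether an unscheduled count is a visit. Protocol Table 5 schedules one Visit 4 and no recheck, and unscheduled visits are mentioned only for health-economic data. Programming rules and table shells are in separate documents (SAP 9 and 11). If rechecks are not visits, or nobody is delayed, nothing is lost. This stands: what is shown is a possible loss, not a certain one.

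Second, the table estimates the proportion at each visit, and for Visit 4 the last count before the procedure fits the Procedure Day definition. The 2% is a modelling aim, not an endpoint or success criterion, and SAP 5.8 already allows further exploratory analyses. This also stands, and it is why the Visit 4 rule should stay. It does not supply a planned count of subjects who ever exceeded 200, the quantity the dose rationale refers to.

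A reader might also infer that neither document specifies any summary able to recover the count. That goes too far: the DSMB percentage could, and the Doppler summary in the protocol synopsis would be an indirect marker. Nor do the documents support reading this as a gap in thrombosis reporting, since thromboembolic events are summarized separately (SAP 5.6.6.1).

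**Conclusion.** The point holds as a minor one. Provided the recheck is recorded and treated as a visit, SAP 8.1 replaces a count above 200 with a later one below 200 for a non-transfused subject whose procedure was delayed, and no final-analysis summary specified in the SAP counts that subject as having reached 200. The by-visit ≥200 proportion can then be too low as a measure of how many subjects exceeded 200.

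The documents do not give the share of subjects delayed and rechecked. If the design projection of under 2% is roughly right, the number affected is probably zero or one to two per cohort. One lost subject changes the displayed cohort figure by about 1.5 points. At these numbers the intervals are too wide to settle whether the 2% aim was met, so what changes is the displayed figure rather than any firm inference. The table is exploratory and no confirmatory test changes.

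**What to change.** Keep the Visit 4 rule in SAP 8.1 for the secondary endpoints. Add to SAP 5.4.3.2 or 5.6 one descriptive table: the number and percentage of subjects with any recorded post-baseline local platelet count ≥200, and >200, before any platelet transfusion, by treatment group within each cohort and overall. Exact 95% intervals are optional. A sentence in 8.1 saying whether an unscheduled count is a visit would help, but the table does not depend on it.

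The cost is one derived variable and one table. Protocol 9.5.1.5 has local platelet counts entered in the CRF with date and clock time; it does not mention unscheduled counts, so the sponsor should confirm that rechecks are captured. The downside is one extra table and a high-count rate that may look less favourable.
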